Adjusting Insulin Delivery to Activity (AIDA):

Use of Activity Data to Adjust Insulin Pump Therapy for Children with Type 1 Diabetes

AIDA Investigation Protocol

Investigators:

[name]
[name]
[name]
[name]

NCT: 022994479

Version Date: September 21, 2016

Summary/Abstract

Being diagnosed with type 1 diabetes at a young age places a lifelong burden on the child together with new challenges and responsibilities for the parents of that child. New technologies such as continuous glucose monitors (CGM) and high resolution insulin pumps with the ability to deliver the low basal rates required for very young children have reduced the burden, but the pumps need to be carefully configured with some of the setting needing to be subtly adjusted following exercise, which if performed later in the day has been shown to reduce the nighttime basal requirements. Many adults with type 1 diabetes (T1D) are able to intuitively make adjustments based on prior activity; however, parents of younger children may not even be aware of their child's activity levels while at day-care or school. Moreover, the amount and timing of the adjustments are not well defined and may be highly variable between subjects. The present study looks to assess the feasibility of combining new generation activity monitors (FitBit or similar), with data obtained from CGM and insulin pump records to improve insulin dose adjustments and prevent hypoglycemia in the pediatric population.

Abbreviations: SAP – sensor augmented pump therapy; CGM – continuous glucose monitor; T1D – type 1 diabetes; TDD – total daily dose;

1. Specific Aim:

To determine the feasibility of using activity monitor data to predict the need to make temporary insulin pump dose adjustments to prevent nighttime hypoglycemia.

2. Background and significance

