The initial 2 weeks of a subject's enrollment in the study will be used to establish his or her baseline activity level and no changes to the insulin regimen will be made based on the activity monitor data. During weeks 3-6 to 12-16, activity data will be reviewed daily and an alternate basal insulin rate will be recommended on days considered to be increased activity days. We will use an adaptive algorithm to help guide suggested nighttime insulin basal rate changes. All recommendations will be reviewed and approved by a study physician prior to implementation. The alternate rate will be derived using the subject's usual care pump settings as an initial starting point from which to make incremental changes in the 3 hour interval leading up to the hypoglycemic event. Target will be the overnight nadir obtained with usual care settings. Residual error (CGM-target) will be used to assess the validity of using the 3 hour window prior to the event to effect lower basal. The patient's primary diabetes team will be informed about the recommended nighttime basal insulin dose change and this will be documented in the patient's medical record in powerchart. The primary diabetes team will not give recommendations regarding nighttime insulin rate dose changes based on activity monitor data; however, they will continue to guide all other aspects of the patient's diabetes management.

b. Patient Selection and Inclusion/Exclusion Criteria

Subjects will be recruited from the outpatient endocrinology clinic based on physician recommendation and approval to approach at Boston Children's Hospital (BCH) as well as through public notice. 20 subjects will be recruited in two different age designations.

Inclusion Criteria:

- Age: 1 to 17 years old
- Type 1 diabetes (as clinically diagnosed by outpatient endocrinologist).
- Treated with insulin pump therapy for greater than or equal 3 months

- Families will need to have access to Wi-Fi and a compatible smartphone in order for the data from the activity monitor and other devices to be transmitted to the research team

Exclusion Criteria:

- Current glucocorticoid use or other medication known to affect insulin action at investigator's discretion.
- Hospitalization within the last month

c. **Description of Study Treatments and Procedures**

RECRUITMENT, SCREENING AND CONSENT:

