This is a pilot study to determine the feasibility of combining activity monitor data with CGM and pump data to make prospective recommendations to reduce basal insulin delivery following high activity days. There is no planned hypothesis for the pilot phase; however, planned comparisons for a larger study will be powered from the data obtained. The primary endpoint for the larger study will be a reduction in the incidence of nighttime hypoglycemia. Secondary outcomes will include the ability of activity data to predict nighttime nadir glucose.

Hypoglycemia will be defined as home meter glucose < 70 mg/dl for all subjects, CGM values below threshold for >30 minutes with no concomitant blood sugar reading (i.e. subject is sleeping at home and ignores the low glucose

alarm but the CGM is <70 for more than 30 minutes). Hypoglycemia episodes within one hour of each other will be considered as one event. Two hypoglycemic events with an intermittent blood glucose value above 70 mg/dL will be treated as a single event. Hypoglycemia and “use-of-supplemental- carbohydrate-to-prevent-hypoglycemia” will be treated identically.

5. Data Management and Statistical Analysis

One study folder, with IRB approved consent forms and case report forms (CRF), will be maintained for each subject recruited into the study. Sensor information, as provided by the manufacturer, will also be recorded on CRFs (identification numbers such as lot or serial together with expiration). Electronic data downloads for the insulin pump, containing a history of insulin delivery commands; glucose meter and glucose sensor, containing a record of all glucose values received and any alarms will be obtained weekly and the downloaded files copied to a password protected study computer in subdirectory labeled with the patient identification number. A copy of the spreadsheet used to screen blood glucose and activity data will also be placed in this directory.

a. Data Analysis Plan

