Data analysis will begin by calculating the baseline (average and standard deviation) activity level for each subject during the first two to six weeks. High activity days will be defined as any day where the activity is greater than one standard deviation above the mean. Correlations will be performed to assess if there is relationship between daytime activity (8- am to 9 pm) and nighttime nadir blood glucose level (continuous). Nadir glucose will also be categorized as hypo- or no-hypo (binary), with a binary logistic regression model used to assess the significance of daytime activity, insulin dosing, and carbohydrate intake, as independent factors increasing the risk of hypoglycemia. Analysis will proceed with generalized estimating equations (not powered but in preparation of the larger study to be conducted). Characteristics of the nighttime glucose profile (nadir glucose, time in target, time below target) will be calculated weekly, with mean and 95% confidence plotted by week. In the event usual-care pump settings are adjusted during the course of the study, the average nighttime glucose values observed for the week following the most recent adjustment will be compared to average values obtained during the final week (assures improvements are due to the availability of the FitBit data rather than the CGM data). Chi2 analysis will be used to assess differences in the incidence of hypoglycemia. Statistical analyses will be performed both as intention to treat and per protocol. The intention to treat analysis will include all data; per protocol analysis will exclude cases in which the subject does not comply with recommendations of the study team or does not complete all 12 weeks of the study. The algorithm will be considered feasible if all data can be assembled, and recommendations deemed reasonable (accepted) in a majority of cases.

Statistical Power and Sample Considerations

This is a feasibility study and therefore is not powered; however, the choice of 10 subjects with any one group is generally considered acceptable for feasibility/pilot-studies and should provide sufficient data to power a larger study.

Study Organization

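### Section 5a does not make the activity–nadir association a within-child estimate, and does not separate nights before and after activity-based basal changes

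*Combined protocol and SAP*

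**What the plan says.** - **Aim (section 1):** the feasibility of "using activity monitor data to predict the need to make temporary insulin pump dose adjustments to prevent nighttime hypoglycemia".
- **Outcomes (section 4d):** the pilot has no planned hypothesis, and its data are to power a larger study. "Secondary outcomes will include the ability of activity data to predict nighttime nadir glucose".
- **Design (section 4a):** no activity-based change is made in the first 2 weeks. After that, "an alternate basal insulin rate will be recommended on days considered to be increased activity days".
- **Continuous analysis (section 5a):** "Correlations will be performed to assess if there is relationship between daytime activity" (8 am to 9 pm) and nighttime nadir. Nothing more is said about this analysis. Section 4a collects both steps and calories, and 5a does not choose between them.
- **Binary analysis (section 5a):** a logistic model for hypoglycemia, "used to assess the significance of daytime activity, insulin dosing, and carbohydrate intake, as independent factors". The next sentence is "Analysis will proceed with generalized estimating equations (not powered but in preparation of the larger study to be conducted"), with no outcome, cluster, working correlation or form of activity.
- **Data sets (section 5a):** "The intention to treat analysis will include all data". The per-protocol analysis excludes non-compliance with recommendations and failure to complete 12 weeks.
- **Own-baseline scaling:** sections 4c and 5a use the child's own mean and SD to flag high-activity days. They do not say it applies to the correlation.

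**The concern.** The clinical question is whether a child's nadir is lower after that child's more active days. Section 2 asks about instances when settings need adjusting, and section 3 has the physician discuss any relationship with the individual patient. Two features of 5a can separate the reported association from that quantity.

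1. **Exposure mixed with intervention.** After baseline, the days with high activity are the days on which the alternate basal is recommended. An all-nights analysis therefore combines the effect of activity with the change meant to offset it. The better the change works, the weaker activity looks as a predictor. The per-protocol set does not remove this, since it keeps those who followed the recommendations.
2. **Differences between children.** With ages from 1 to 17, habitual activity and habitual nadir may both differ between children. If raw child-nights are pooled, those differences enter the correlation. They can produce an association with no within-child relation, or mask a real one.

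At stake is the nadir estimate, which bears on the aim and on a listed secondary outcome of the larger study.

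**Working it through.** The plan gives no alpha, effect size or variance for this analysis, so there is no figure to reproduce.

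**Inputs from the documents:** 20 children; 14 baseline days; 12 to 16 weeks, so 84 to 112 nights; a high-activity day is one above the child's own mean + 1 SD.

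**Assumed (not in the documents):** all intraclass correlations (ICC), correlations, slopes and nadir rises below. Slopes are in night-to-night SD units.

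**Step 1: dilution by basal changes.** Let within-child activity be standard normal with true slope β = -0.30. Suppose the alternate rate raises nadir by δ on high-activity nights, over a share f of all nights. The child-centred all-nights slope is then β + δ·f·φ(1), where φ(1) = e^(-0.5)/√(2π) = 0.242.

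| Change starts | f | δ = 0.3 | δ = 0.6 | δ = 0.9 |
|---|---|---|---|---|
| Night 15, formula | 70/84 = 0.833 | -0.24 | -0.18 | -0.12 |
| Night 15, simulated | | -0.237 | -0.177 | -0.114 |
| Night 43, formula | 42/84 = 0.5 | -0.26 | -0.23 | -0.19 |
| Night 43, simulated | | -0.263 | -0.225 | -0.188 |

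Example: -0.30 + 0.6 × 0.833 × 0.242 = -0.18. This step does not depend on pooling. In mg/dL, an assumed true slope of -8 per SD of activity falls to -6.7, -5.4 or -4.0 if the change cancels 50, 100 or 150% of the activity effect on flagged nights.

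**Step 2: pooled raw correlation, no within-child effect.** With child-level correlation r_b and within-child correlation r_w, pooled r ≈ r_w√[(1-ICCx)(1-ICCy)] + r_b√(ICCx·ICCy). At r_b = 0 the mean r is 0, but the variance is inflated by about 1 + (n-1)·ICCx·ICCy. For ICCs (0.5, 0.2) and n = 84: 1 + 83 × 0.10 = 9.3; 1.96/√9.3 = 0.64; two-sided rejection 52%. Simulated rejection at nominal 5%:

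| ICC (activity, nadir) | 84 nights, r_b = 0 | 84 nights, r_b = -0.5 | 14 nights, r_b = 0 | 14 nights, r_b = -0.5 |
|---|---|---|---|---|
| 0.05, 0.05 | 7.5% | 18.9% | 5.4% | 7.3% |
| 0.3, 0.02 | 10.6% | 35.0% | 6.5% | 11.7% |
| 0.3, 0.1 | 27.6% | 76.0% | 9.2% | 30.7% |
| 0.5, 0.2 | 50.0% | 92.8% | 19.9% | 64.0% |
| 0.6, 0.3 | 62.3% | 95.9% | 27.1% | 79.5% |

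Child-centred tests reject in 3.8–5.7%. Masking, with r_w = -0.15 and r_b = +0.5: for (0.5, 0.2) the formula gives -0.095 + 0.158 = +0.06. The simulated mean pooled r is -0.04, +0.05 and +0.12 for the last three ICC pairs.

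**Step 3: does naming GEE settle it?** Simulated rejection with no within-child effect and r_b = -0.5, for ICCs (0.3, 0.1) and (0.5, 0.2):

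| GEE specification | 84 nights | 14 nights |
|---|---|---|
| Raw activity, independence | 38.7%, 50.0% | 19.0%, 36.3% |
| Raw activity, exchangeable | 6.7%, 5.3% | 12.3%, 18.0% |
| Own deviation + child mean | 3.7%, 4.0% | 6.3%, 3.7% |

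The answer depends on choices that 5a does not state.

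**Step 4: which nights give a clean estimate?** Nights up to each child's first basal change look natural. But section 4c triggers the change from nadirs on high-activity days, so the cut-off depends on the outcome. Children with strong effects leave early. With a true mean slope of -0.30 and an assumed between-child slope SD of 0.30–0.45:

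- nights before first change: about -0.22 to -0.13
- fixed first 14 days: about -0.29 to -0.30
- all nights with an alternate-basal indicator: about -0.26 to -0.29

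**Precision.** The SE of the 14-day slope is about √[1/(20 × 13) + s²/20], with s the slope SD. It is 0.06 at s = 0 and 0.12 at s = 0.45, in line with the simulated 0.06 and 0.07–0.13.

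**The case against.** The strongest reply is that this is an exploratory correlation in an unpowered pilot with no planned hypothesis. Feasibility is judged on assembling data and acceptance of recommendations. The larger study's primary endpoint is the incidence of nighttime hypoglycemia, not a correlation, and physicians must approve every recommendation. The plan already names GEE, has insulin dosing in the logistic model, and begins by computing each child's own activity mean and SD. All magnitudes above are assumed. These points stand and limit the consequence. They do not supply a within-child nadir estimate: GEE and insulin dosing are attached to the logistic model, no within/between split is stated anywhere, and Step 1 applies even to a perfectly child-centred correlation.

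A reader might infer more than the documents support:

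- **That no night set is given.** The all-data rule supplies one. What is missing is the separation of nights before and after activity-based changes.
- **That the plan pools raw steps or calories.** It neither says so nor excludes it. Per-child correlations are equally possible, though then no rule combines them.
- **That repeated nights are ignored throughout.** GEE is named; its scope and form are not.
- **That the chi-square test is also invalid.** "Chi2 analysis will be used to assess differences in the incidence of hypoglycemia" does not name its contrast. For the one period comparison in 5a (one week against the final week), level differences between children do not inflate it: simulated rejection was 3.2% with 7 nights per period. No error is shown there.

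**Conclusion.** The concern holds in a limited form and should be acted on. Section 5a leaves the activity–nadir analysis without a unit, a child-level scaling or a separation of treated from untreated nights, although the aim is a within-child one.

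- **Dilution** follows from the all-data rule combined with the section 4a recommendation, provided changes are made and raise nadir. An assumed slope of -0.30 falls to between about -0.26 and -0.11, depending on start and effect of the change.
- **Confounding by child** is conditional on pooling raw child-nights. False-positive rates at 84 nights then run from 7% to 62% with no child-level correlation and from 19% to 96% at -0.5. The low end is nearly harmless, and the documents give no basis for placing the trial within the range.

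It would be tempting to conclude that the pilot's feasibility conclusion is compromised. It is not: that criterion does not use this estimate. Confidence is medium, because the structure is clear from the text but every size is assumed.

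**What to change.** Replace the correlation sentence in section 5a with text such as:

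> The activity–nadir association will be estimated on child-nights by GEE (identity link, cluster = child, exchangeable working correlation, small-sample-corrected robust variance). Activity (one named measure, steps or calories) enters as two terms: the day's deviation from the child's own mean, and the child's mean. The main estimate uses the fixed first 14 days of each child, when no activity-based change is made. A supporting all-data estimate uses all nights with an indicator for nights on which the alternate basal was in use. The planned logistic GEE for hypoglycemia uses the same activity terms and indicator and keeps insulin dosing and carbohydrate intake.

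Do not define the main set as nights up to each child's first basal change (Step 4). Correlations may stay as per-child descriptive summaries. No change to the chi-square analysis is asked for here.

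**Cost:** a few sentences, modest extra analysis and no new data. The 14-day estimate is less precise: simulated SE about 0.06, or 0.07–0.13 if slopes vary between children, against about 0.03, or 0.05–0.11, for the all-nights indicator model. The indicator model in turn assumes a linear activity effect and is slightly attenuated if slopes vary, which is why it supports the main estimate and does not replace it.

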To identify high activity days, subjects will be provided with activity monitors (FitBit or similar). These monitors have become popular but are not medical devices *per se*; thus, we will be taking care not to rely solely on the device for identifying high activity days. While not approved as a medical device, our evaluation of one device (FitBit) indicated it could provide a reasonable estimate of the number of calories burned and steps taken and that the data was easily accessed through the cloud (Figure 2). Other research groups have used similar devices to show days that include 30 min of moderate to vigorous physical activity are followed by a 31% increase in hypoglycemia (95% CI 1.05–1.63; $P = 0.017$)(3).

[figure not shown]

Figure 3. FitBit activity data obtained from cloud.

The devices are small (about the size of a quarter) and rely on accelerometers to estimate activity. They are, however, subject to errors whenever the activity does not involve acceleration of the device *per se* (e.g. riding a stationary bike). Software provided with the devices allows these events to be separately tracked. Still, published studies have validated that these devices provide objective, reliable assessments of activity completed and calories expended per day (14-17). Therefore, we believe that they will provide a more reliable estimate of activity than can be inferred from log-book records, and allow us to assess the validity of using daytime activity to effect changes in nighttime insulin basal rates. However, changes in the rates will not be recommended to the patient without physician approval. Rather, if we determine a relationship between high daytime activity and low overnight basal requirements, the physician will discuss with the patient how best to identify days involving high activity without relying solely on FitBit device.

4. Design and Methods

a. Study design

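### Continuous nadir glucose, listed as a secondary outcome, has no stated covariate-adjusted analysis: insulin and carbohydrate enter only the hypo/no-hypo logistic model

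*Combined protocol and SAP*

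**What the plan says.** Section 4.d makes a reduction in the incidence of nighttime hypoglycemia the primary endpoint of the larger study and then adds: "Secondary outcomes will include the ability of activity data to predict nighttime nadir glucose". It does not say whether that secondary outcome belongs to the pilot or the larger study, but the larger study is to be powered from the pilot's data in any case.

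Section 5.a plans these analyses of the nadir:

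- A correlation on the continuous scale: "Correlations will be performed to assess if there is relationship between daytime activity (8- am to 9 pm) and nighttime nadir blood glucose level (continuous".
- A logistic model on the categorized scale: "Nadir glucose will also be categorized as hypo- or no-hypo (binary), with a binary logistic regression model used to assess the significance of daytime activity". Its factors are "daytime activity, insulin dosing, and carbohydrate intake, as independent factors increasing the risk of hypoglycemia".
- A GEE step: "Analysis will proceed with generalized estimating equations (not powered but in preparation of the larger study to be conducted".
- Weekly means with 95% confidence for nadir glucose, time in target and time below target. These describe the nights and do not relate them to activity.

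Section 4.d defines the event: "Hypoglycemia will be defined as home meter glucose < 70 mg/dl for all subjects, CGM values below threshold for >30 minutes" where there is no accompanying blood glucose reading. Carbohydrate taken to prevent hypoglycemia and hypoglycemia itself "will be treated identically".

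**The concern.** The background section wants activity data to show when pump settings need changing and also how large the change should be. An adjusted effect in mg/dL, with its residual variance, speaks to size and would help plan any later study of nadir prediction. As written, insulin and carbohydrate are accounted for only after the nadir has been reduced to two categories. On a simple cut at 70 mg/dL, a night at 71 counts the same as one at 180, and a night at 69 the same as one at 40.

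The correlation has a different weakness. After baseline the study itself recommends an alternate basal rate on high-activity days, so insulin and activity move together by design. With 20 children, precision is scarce, and the adjusted estimate is one of the things the pilot could pass on.

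**Working it through.** **What each analysis in 5.a covers**

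| Analysis | Outcome | Factors named |
|---|---|---|
| Correlation | continuous nadir | daytime activity |
| Logistic regression | hypo/no-hypo | activity, insulin dosing, carbohydrate |
| GEE | not stated | not stated (link also not stated) |
| Weekly summaries | nadir, time in and below target | none |

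No line states an adjusted analysis of the continuous nadir. Only a generous reading of the GEE sentence would supply one.

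**Why the correlation cannot stand in.** Sections 4.a and 4.c provide for a lower basal rate after high-activity days once baseline is over. If activity lowers the nadir and the reduced basal raises it, the two effects offset each other in an unadjusted correlation, and a real activity effect may look small or absent. This would not arise if the correlation used baseline nights only, but 5.a sets no such limit.

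**Information kept by the two-category outcome.** The plan gives no power, effect size, nadir SD or rate of hypoglycemic nights, so there is no figure of its own to reproduce. Let p be the share of nights classed as hypoglycemic (assumed), z the normal quantile at p, and φ the normal density. If activity shifts a normal nadir distribution without changing its shape, the efficiency of the binary analysis relative to the continuous one is

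E = φ(z)² / [p(1 − p)].

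For p = 0.20: φ(−0.842) = 0.2800, so E = 0.0784 / 0.16 = 0.490.

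| p | φ(z) | E | Information lost |
|---|---|---|---|
| 5% | 0.1031 | 0.224 | 78% |
| 10% | 0.1755 | 0.342 | 66% |
| 20% | 0.2800 | 0.490 | 51% |
| 30% | 0.3477 | 0.576 | 42% |
| 40% | 0.3863 | 0.622 | 38% |
| 50% | 0.3989 | 0.637 | 36% |

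The loss reaches one half only when p is about 0.209 or lower. As relative standard errors, the range is 1/√0.637 = 1.25 to 1/√0.224 = 2.11.

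**Check with clustered nights.** A simulation of 20 children × 84 nights = 1,680 nights (12 weeks × 7) compared exchangeable linear and logistic GEEs with three covariates. It assumed an ICC of 0.15 and an activity effect of 0.1 SD per SD, with 100 runs per rate. Relative efficiency was 0.30, 0.40, 0.58 and 0.55 at p = 10%, 20%, 30% and 40%. The pattern matches the table, with Monte Carlo noise. The activity effect was held constant, so this checks the formula and does not model the weeks when basal insulin is being changed.

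**Allowing for treated nights.** Section 4.c sets a 60 mg/dL alarm and has hypoglycemia treated at home, and preventive carbohydrate counts as an event, so some low nadirs are altered. A further check assumed:

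- nadir SD 40 mg/dL and no covariate adjustment;
- carbohydrate on 30–50% of nights heading below 80 mg/dL, raising the nadir by 30–50 mg/dL;
- a treated floor of 55 mg/dL;
- high-activity and other nights in equal numbers;
- a risk ratio of 1.31, from the section 3 statement that such days "are followed by a 31% increase in hypoglycemia (95% CI 1.05–1.63; $P = 0.017$)(3".

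At p = 20% the high-activity rate is 0.20 × 1.31 = 0.262, so the true shift is 40 × (0.842 − 0.637) = 8.2 mg/dL. The observed shift falls to 5.8–6.7 mg/dL, and the information loss falls from 48% to 31–42%. At p = 30% the loss is 14–32%. A smaller share of high-activity nights raises these losses by a few points.

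**The case against.** The case for leaving the plan alone has real substance.

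- **The binary model has a stated purpose.** Incidence of nighttime hypoglycemia is the larger study's primary endpoint, and powering it needs event-scale estimates. This stands. A reader might infer that the logistic model should be demoted to a supporting role, but that would rank a secondary outcome above the primary endpoint.
- **The pilot has no hypothesis and is not powered.** Feasibility is judged on assembling the data and having recommendations accepted. This also stands, so no pilot conclusion turns on this model. It limits the weight of the point but does not remove it, because the pilot exists to supply estimates.
- **The GEE sentence may already cover the continuous nadir.** It may. The gap is then partly one of specification, and the same edit closes it.
- **The event is not a bare cut at 70 mg/dL.** The 30-minute sensor rule and the carbohydrate rule make the normal-theory loss approximate, and a linear model of treated nadirs would be attenuated. This stands and is reflected in the smaller losses above.

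Three stronger readings are tempting and not supported. The first is that half or more of the information is lost: that needs a hypoglycemic-night rate of about 21% or less, which the documents do not give. The second is that power is roughly halved. Simulations using a risk ratio of 1.31 over 84 nights gave 34% against 68% at a 10% rate and 61% against 89% at 20% (binary against continuous), but they ignore the basal changes made after baseline. On the 14 baseline nights alone both models are weak: 8% against 18%, and 15% against 22%. The third is that the dosing algorithm needs a pooled mg/dL coefficient. It works from each child's own nadir and deviation from target, so none enters it.

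**Conclusion.** The point holds as a gap in the stated analyses. The nadir-prediction outcome has a correlation with no covariates named, and the adjusted model that is named uses a coarser outcome. Relying on that model costs about 36% to 78% of the information on activity for hypoglycemic-night rates from 50% down to 5%, assuming a normal location shift. In the one treated-nights scenario checked, the loss was 14–42% at rates of 20–30%. It would also be smaller if activity affects only the lower tail. The rates, nadir SD, ICC and treatment pattern are all assumptions.

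The confounding of the correlation rests on two conditions: that recommended basal changes are followed, and that nights after baseline are included. The change is worth making because it is cheap and uses data already collected. It does not affect the pilot's feasibility conclusion.

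**What to change.** In section 5.a:

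1. Add an identity-link GEE, or a linear mixed model with a child effect, of continuous nadir glucose on daytime activity, insulin dosing and carbohydrate intake. Name it as the adjusted analysis of the nadir-prediction outcome. Report the adjusted mg/dL effect of activity with its 95% CI and the residual variance.
2. State that the insulin term includes the overnight basal rate in use, so that the alternate profile is accounted for.
3. Keep the logistic GEE alongside it as the analysis for the larger study's incidence endpoint, and state the outcome, link and covariates of each GEE.
4. Flag nights with preventive or treatment carbohydrate. Add a sensitivity analysis that excludes those nights or treats their nadirs as censored. Check skewness and the sensor floor.

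The cost is a few sentences and one extra model with its checks, with no new data or visits. The downside is small: the mg/dL effect may be attenuated on treated nights, which the sensitivity analysis should help to show.
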